1.2.2 Overview of EPO

The process of erythropoiesis in the bone marrow takes 14–17 days and is highly dependent on a number of hemopoietic growth factors. Erythropoietin (EPO) alone, or in combination with other colony-stimulating factors (CSFs), has therefore been investigated as a potential approach to correct the anemia associated with MDS. Although it is not approved in MDS, the guidelines for treatment of MDS patients, e.g. NCCN Guidelines, recommend the use of EPO in lower risk MDS patients with symptomatic anemia and endogenous EPO levels ≤ 500 mU/mL.

In the EPO treatment and monitoring guideline published by David Mc Culloch in 2010, EPO is also indicated in patients with anemia caused by MDS ([Appendix 3](#)).

Treatment with EPO as monotherapy may induce erythroid responses in 16–30% of patients with low-risk MDS ([Hellström-Lindberg 2005](#)). One placebo-controlled randomized study demonstrated an overall positive effect in the EPO-treated cohort, however, at the subgroup level, only patients with FAB RA, and patients without transfusion need showed a significant response to treatment (Italian Cooperative Study Group for rHuEpo in Myelodysplastic

Syndromes 1998). Several smaller phase II studies have indicated that patients with low pre-treatment serum EPO levels (<150–200 U/L) are particularly likely to benefit (Hellström-Lindberg 2005).

A meta-analysis of 205 patients from 17 studies revealed an overall response rate of 16%, and showed that patients with no transfusion requirement and MDS other than RARS were more likely to benefit from treatment than other patient types (Hellström-Lindberg 1995). There is no consistent information as to the optimal duration of treatment necessary to assess a response to treatment. While the majority of studies have treated patients for 12–16 weeks, a few trials have reported that additional responses may be observed if treatment is pursued for as long as 6 months (Terpos 2002). The effect of the new long-acting darbepoetin-alfa has been assessed in some recent trials, and it has been found to be at least as effective as EPO (Mannone 2006, Stasi 2005).

Therapy with EPO increases the risk for thrombo-embolic events, including deep-vein thrombosis, pulmonary emboli, stroke and myocardial infarction. Other adverse events linked to EPO therapy are hypertension, flu-like symptoms, arthralgia and dermatological reactions.

2 Rationale

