Patients who do not respond to 12-week-EPO treatment will be switched to the combination for another period of 12 weeks. The analysis of those patients after the cross-over to the combination will allow understanding if the addition of DFX to EPO is efficacious in patients who are already non-responders to EPO.

In summary, the open label, randomized design and the schedule of assessment are appropriate for this study and are according to the current standards of care.

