4.1 Description of study design

This is an open-label, phase II, randomized, multi-center, pilot study to assess the efficacy in terms of erythroid improvement of DFX combined with EPO compared to EPO alone in patients with low- and int-1-risk MDS.

Patients will be randomly assigned to DFX plus EPO 40,000 units/week or to EPO 40,000 units/week alone in a 1:1 ratio. The dose of DFX DT will be 10 mg/kg/day and the dose of DFX FCT will be 7 mg/kg/day. At the time when DFX FCT study drug becomes available at a study site, all new patients who are randomized to combination therapy will receive the DFX FCT. Patients who are ongoing and receive DFX DT will continue with the DT. It is not permitted to change formulation during treatment. EPO dose changes after 4 and 12 weeks of study treatment will also be performed in both arms according to the EPO guidelines.

If after 4 weeks, increase in Hb is < 1 g/dL and total Hb is < 12 g/dL, the EPO dose will be increased to 60,000 units/week. If increase in Hb is ≥ 1 g/dL and total Hb is < 12 g/dL, patients will continue the current EPO dose. If Hb increase is ≥ 1 g/dL and total Hb is ≥ 12 g/dL, the patients will hold EPO treatment until end of study (Table 4-1).

If after 12 weeks of treatment with EPO alone, Hb increase is < 1 g/dL and total Hb is < 12 g/dL, the patient will switch to the combination therapy with EPO and DFX. If increase in Hb is ≥ 1 g/dL and total Hb is < 12 g/dL, patients will continue the current EPO dose. If Hb increase is ≥ 1 g/dL and total Hb is ≥ 12 g/dL, the patients will hold EPO treatment until end of study (Table 4-1).

[figure not shown]
If after 12 weeks of treatment with EPO in combination with DFX, Hb increase is < 1 g/dL and total Hb is < 12 g/dL, the patient will be discontinued from the study. If increase in Hb is ≥ 1 g/dL and total Hb is < 12 g/dL, patients will continue the current EPO dose plus DFX. If Hb increase is ≥ 1 g/dL and total Hb is ≥ 12 g/dL, the patients will hold EPO dose and receive treatment with DFX alone.

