10.4.2 Statistical hypothesis, model, and method of analysis

[figure not shown]
A patient is defined as an erythroid responder if the criterion of Hb increase from baseline ≥ 1.5 g/dL is met at any time within the first 12 weeks period. Baseline is defined as the last available Hb value available within windows of 4 weeks prior to or on treatment start date. No imputation will be performed for missing laboratory data.

Difference in proportions between treatment groups with its 95% Agresti-Caffo ([Agresti-Caffo 2000](#)) confidence interval will be provided. Erythroid response proportion will be also summarized by treatment group with its 95% Clopper-Pearson confidence intervals. Analysis will be performed on FAS and PP set.

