Hematological response: If a patient fulfills at least erythroid or platelet or neutrophil response as well as it's corresponding pre-treatment condition	Hb < 11 g/dL at baseline Platelet $< 100 \times 10^9/L$ at baseline Neutrophil $< 1.0 \times 10^9/L$ at baseline	Hb increase from baseline by ≥ 1.5 g/dL Increase from baseline $\geq 30 \times 10^9/L$ Increase from baseline $> 100\%$ and increase from baseline $> 0.5 \times 10^9/L$	Erythroid response Platelet response Neutrophil response
Hematologic improvement: If a patient fulfills at least platelet or neutrophil improvement response without it's corresponding pre-treatment condition	Platelet $\geq 100 \times 10^9/L$ at baseline Neutrophil $\geq 1.0 \times 10^9/L$ at baseline	Increase from baseline $\geq 30 \times 10^9/L$ Increase from baseline $> 0.5 \times 10^9/L$	Platelet improvement Neutrophil improvement

10.5.2 To assess the effect of treatment on erythropoiesis within 24 weeks in patients who were non-responder to EPO alone after 12 weeks and switched to DFX+EPO

Patients who are non-responders to erythroid at week 12 in the EPO group will have to switch to combination therapy, if they continue to participate in the study.

Patients meeting the criterion (Hb increase from baseline ≥ 1.5 g/dL) at any time between week 12 and week 24 will be considered as erythroid responders.

Proportion of erythroid responders between week 13 and 24 will be reported along with its 95% Clopper-Pearson confidence interval. Descriptive statistics will be provided for erythroid response. Analysis will be performed on FAS and PP set.

10.5.3 To assess time to erythroid response in patients treated with DFX+EPO and patients treated with EPO alone

This analysis will include patients who were randomized to EPO and EPO+DFX and remained in their respective treatment arms. Descriptive statistics will be provided for erythroid responder patients (achieved Hb increase ≥ 1.5 g/dL from baseline) for time to response (days), defined as the time from date of start of treatment to the date of event defined as the first documented erythroid response between week 1 to week 24. Analysis will be performed on FAS and PP set for both treatment groups.

10.5.4 To assess the effect of treatment with EPO alone on erythropoiesis after 24 weeks of treatment

[figure not shown]
This analysis includes patients who started with the EPO alone and are not switched to combination therapy.

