	Pre-treatment conditions	Post-baseline	Response
Hematological response: If a patient fulfills at least erythroid or platelet or neutrophil response as well as it's corresponding pre-treatment condition	Hb < 11 g/dL at baseline	Hb increase from baseline by ≥ 1.5 g/dL	Erythroid response
	Platelet < 100×10^9 /L at baseline	Increase from baseline $\geq 30 \times 10^9$ /L	Platelet response
	Neutrophil < 1.0×10^9 /L at baseline	Increase from baseline > 100% and increase from baseline > 0.5×10^9 /L	Neutrophil response
Hematologic improvement: If a patient fulfills at least hemoglobin or platelet or neutrophil improvement response without it's corresponding pre-treatment condition	Hemoglobin < 11 g/dL at baseline	Increase from baseline by ≥ 1 g/dL	Hemoglobin improvement
	Platelet $\geq 100 \times 10^9$ /L at baseline	Increase from baseline $\geq 30 \times 10^9$ /L	Platelet improvement
	Neutrophil $\geq 1.0 \times 10^9$ /L at baseline	Increase from baseline > 0.5×10^9 /L	Neutrophil improvement

2.9.2.2 To assess the effect of treatment on erythropoiesis within 24 weeks in patients who were non-responder to EPO alone after 12 weeks and switched to DFX+EPO

Patients who are non-responders to erythroid at week 12 in the EPO group will have to switch to combination therapy, if they continue to participate in the study.

Patients meeting the criterion (Hb increase from baseline ≥ 1.5 g/dL) at any time between week 12 and week 24 will be considered as erythroid responders.

Proportion of erythroid responders between week 13 and 24 will be reported along with its 95% Clopper-Pearson confidence interval. Descriptive statistics will be provided for erythroid response. Analysis will be performed on FAS.

2.9.2.3 To assess the effect of treatment with EPO alone on erythropoiesis within 24 weeks of treatment

This analysis includes patients who started with the EPO alone and are not switched to combination therapy.

Patients meeting the criterion (Hb increase from baseline ≥ 1.5 g/dL) at any time between week 1 and week 24 will be considered as erythroid responders. Proportion of erythroid responders who starts with EPO alone and are not switched to combination therapy will be reported along with its 95% Clopper-Pearson confidence interval.

Descriptive statistics will be provided for erythroid response. Analysis will be performed on FAS.

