4.2.9 Baseline

In general, for safety variables, the baseline value is defined to be the last available value prior to or on the day of first dose of study drug. For efficacy variables, the baseline value is defined to be the last available value prior to or on the day of randomization.

This definition does not apply for the following exceptions, where a specific definition was used:

- Serum creatinine: baseline value is defined as the mean of visit 1 and 2.
- Serum ferritin: baseline value is defined as the mean of visit 1 and 2.

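### The uncontrolled switch phase cannot show whether adding DFX works in EPO non-responders, although Protocol 2.2 says it will

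*Protocol*

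**What the plan says.** Protocol 2.2 gives the purpose of the cross-over: the analysis after the switch "will allow understanding if the addition of DFX to EPO is efficacious in patients who are already non-responders to EPO".

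The rules that govern that analysis are these.

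- **Who switches.** Protocol 4.1: "If after 12 weeks of treatment with EPO alone, Hb increase is < 1 g/dL and total Hb is < 12 g/dL", the patient moves to EPO plus DFX. Table 4-1 and SAP Table 2-1 apply this to the whole EPO arm. Combination-arm patients with the same Hb status leave the study.
- **Who responds.** Protocol 10.5.2 requires a rise of at least 1.5 g/dL from baseline; patients who reach it "at any time between week 12 and week 24 will be considered as erythroid responders". SAP 2.9.2.2 uses the same rule.
- **Which baseline.** Protocol 10.4.2: "Baseline is defined as the last available Hb value available within windows of 4 weeks prior to or on treatment start date". SAP 4.2.9: "For efficacy variables, the baseline value is defined to be the last available value prior to or on the day of randomization". Its listed exceptions are serum creatinine and serum ferritin. Neither document sets a new Hb baseline at the switch.
- **What is reported.** Protocol 10.5.2: "Proportion of erythroid responders between week 13 and 24 will be reported along with its 95% Clopper-Pearson confidence interval", together with descriptive statistics. No comparator, reference rate or test is named.
- **What is known about late response.** Protocol 1.2.2 reports that in a few trials "additional responses may be observed if treatment is pursued for as long as 6 months". It gives no rate.

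**The concern.** The sentence in Section 2.2 attributes an effect to DFX. That needs some estimate of what the same patients would have done on continued EPO, and the plan has none. A switch-phase response can come from DFX, from continued EPO, from late response to the earlier EPO, or from Hb fluctuation around a value already close to the threshold. The plan cannot separate these sources.

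At stake is what may be concluded. If the Section 2.2 sentence is carried into the report, a non-zero response rate and its interval could be offered as evidence that DFX works in EPO non-responders.

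**Working it through.** The plan states no figure for the switch phase, so there is nothing to reproduce. Its only precision figures (Protocol 10.8, SAP 2.11) belong to the week-12 comparison.

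**1. Is there a usable control?** There are three candidates, and none serves.

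- EPO non-responders kept on EPO alone: none is planned, because all who continue are switched (Protocol 4.1, Table 4-1).
- Combination-arm non-responders: discontinued at week 12.
- EPO patients who do not switch: they did not meet the switch rule, and the notes in Protocol 10.5.9 and 10.5.10 describe them as responders only.

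The switch regimen contains EPO (Protocol 4.1, Table 4-1). Protocol 6.1.1 says these patients stop EPO and then that they switch to the combination. Those statements must be reconciled; I follow Section 4.1 here.

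**2. The gap between the two thresholds.** Switching requires a rise below 1 g/dL, and response requires 1.5 g/dL from the same baseline. A patient at +0.9 needs 1.5 − 0.9 = 0.6 g/dL more. Three scheduled readings follow Visit 10: Visit 11 (Day 112), Visit 12 (Day 140) and end of treatment (Day 168). Any one of them is enough.

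For a patient whose true rise stays at 0.9, treating baseline as exact, the chance that at least one of three readings reaches 1.5 is 1 − Φ(0.6/SD)³. This gives 7%, 19% and 31% at within-patient SD 0.3, 0.4 and 0.5.

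**3. Share of switchers counted as responders with no DFX effect.** All inputs are assumptions, because the documents give none:

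- within-patient SD 0.2-0.6 g/dL on every reading, including baseline;
- mean true EPO rise 0.3 or 0.6 g/dL, with between-patient SD 0.6 or 0.8;
- after Visit 10, either no further change or an EPO-only rise reaching 0.3 g/dL in equal steps over the three visits.

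I simulated 1,000,000 patients per setting. A patient switches if the measured Visit 10 rise is below 1, and responds if the highest of the three later readings minus baseline is at least 1.5. The ranges run over the four combinations of mean and between-patient SD.

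| Within-patient SD | No further change | EPO alone adds 0.3 g/dL |
|---|---|---|
| 0.2 | 0.3-0.6% | 1.9-3.5% |
| 0.3 | 1.8-3.2% | 5.1-8.6% |
| 0.4 | 4.4-7.3% | 9.1-14.1% |
| 0.5 | 7.9-12.0% | 13.0-19.3% |
| 0.6 | 11.5-16.5% | 16.9-24.0% |

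**4. What the interval would show.** Sixty patients at 1:1 give 30 on EPO. The 40% reference rate in Protocol 10.8 gives roughly 30 × (1 − 0.40) = 18 switchers. This is approximate, because that rate refers to the 1.5 g/dL criterion and not to the switch rule.

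- Expected responders without DFX: 18 × 0.003 = 0.05 at the lowest rate and 18 × 0.24 = 4.3 at the highest.
- Chance of at least one, 1 − (1 − p)¹⁸: 5% at p = 0.003, 85% at p = 0.10, 99% at p = 0.24.
- Clopper-Pearson 95% limits: 0.1-27.3% for 1/18 and 6.4-47.6% for 4/18.

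One responder puts the lower limit above zero. The interval for 4/18 covers no-DFX rates from 6.4% up to the largest in the table.

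**5. Would a Visit 10 baseline settle it?** No. Visit 10 is the value on which switchers are selected, so low readings are over-represented. With no DFX effect and no further change, the same simulation gives a mean apparent rise from Visit 10 of about 0.07-0.20 g/dL at SD 0.4-0.6.

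**The case against.** The strongest reply is that the causal claim is one rationale sentence and not the analysis. Protocol 10.5.2 and SAP 2.9.2.2 speak of the effect of treatment in switched patients and plan one proportion with an interval, without a test or success rule. The trial is a pilot without a formal sample size calculation, and Section 2.2 gives the question of whether DFX raises the number of EPO responders to the randomized week-12 comparison. All of this stands. A reader might infer that the plan scores switch-phase responders as DFX successes; it does not, and calls them only erythroid responders.

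A reader might also take Section 1.2.2 to establish that late EPO responses will occur. It is hedged: only a few trials are cited, and the section says information on treatment duration is inconsistent. The guideline in Appendix 3 treats a rise below 1 g/dL at week 12, with Hb below 12 g/dL, as non-response. So the week-12 cut is reasoned, but it provides no control.

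The size rests wholly on assumptions. At SD 0.2-0.3 without drift it is at most 3.2%, or 18 × 0.032 = 0.6 of a patient. The 0.3 g/dL drift has no source in the documents. The simulation also keeps patients who had reached 1.5 g/dL before Visit 10, and excluding them lowers the upper figures.

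Finally, Hb by visit for switchers is already planned (Protocol 10.5.10, SAP 2.9.2.5), so a Visit 10 table would only re-express those data. None of these replies supplies the missing comparison, and neither document limits the sentence in Section 2.2.

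**Conclusion.** The point holds as a correction to what may be concluded. The switch phase can describe the response rate on EPO plus DFX after 12 weeks of EPO. It cannot show that DFX is efficacious in EPO non-responders. This follows from the plan's own rules and needs no outside figure.

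The size is uncertain. With no DFX effect, about 0.3-17% of switchers would count as responders without further change, and about 2-24% with an EPO-only rise of 0.3 g/dL, under the assumed SDs and mean rises above. These are illustrations and not estimates for this trial.

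A reader might infer that the trial's main DFX result is compromised or that a redesign is required. The documents support neither: the week-12 comparison is randomized and made before any switch, and the switch-phase analysis is already descriptive.

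**What to change.** Reword the Section 2.2 sentence: the switch phase describes the erythroid response rate on EPO plus DFX after 12 weeks of EPO alone, and cannot separate a DFX effect from continued EPO, late response or Hb variation. Carry that limit as one sentence into Protocol 10.5.2 and SAP 2.9.2.2.

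Optionally, show Hb change from Visit 10 by visit beside the rate from the original baseline. State with it that Visit 10 is the selection value, so regression to the mean produces an apparent rise even without a DFX effect. It should not replace the original-baseline rate.

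A randomized control within the switch group would repair the logic but not the precision. Splitting about 18 patients 9:9 gives roughly 18% power for 10% versus 30%, 30% for 10% versus 40%, and 15% for 20% versus 40%.

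The cost is a weaker claim, three sentences of text and, if used, one descriptive table from data already collected.

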2.3 Rationale for dose and regimen selection

EPO treatment is used in MDS patients early after the diagnosis to induce erythroid response and alleviate the symptoms of anemia. At this stage, iron overload is not expected to be high. In addition, the mechanism by which DFX might be efficacious in this setting is related to the depletion of toxic free iron and possibly to the inhibition of NF- κ B in the malignant cells. High doses of DFX are not required to achieve these objectives. Therefore, the dose of DFX DT is established at 10 mg/kg/day and the dose of DFX FCT is established at 7 mg/kg/day.

The current practice for the use of EPO is so variable and differs among countries and even among physicians. Therefore the dose of EPO in this study is chosen based on the guidelines (ASH-ASCO) published by David McCulloch in 2010. According to that, the starting dose in this study is 40,000 units/week. If increase in Hb is < 1 g/dL and total Hb is < 12 g/dL after 4 weeks, the dose should be increased to 60,000 units/week. If increase in Hb is ≥ 1 g/dL and total Hb is < 12 g/dL, patients should continue the current EPO dose. If Hb increase is ≥ 1 g/dL and total Hb is ≥ 12 g/dL, the patients should hold EPO treatment.

Dose change after 12 weeks of study treatment will also be performed according to the EPO guidelines (Appendix 3). If Hb increase is ≥ 1 g/dL and total Hb is < 12 g/dL, patients should continue the current EPO dose. If Hb increase is ≥ 1 g/dL and total Hb is ≥ 12 g/dL, the patients should hold EPO dose (Table 4-1). According to the EPO guidelines, if after 12 weeks of treatment with EPO, Hb increase is < 1 g/dL and total Hb < 12 g/dL, the patient should discontinue EPO as the patient is not responding. In this study, those patients who do not respond to 12-week-EPO treatment will not be discontinued, but they will be switched to the combination for another period of 12 weeks.

As the EPO guidelines only provide guidance for EPO use: EPO dosing, dose adjustments and dose discontinuation, and do not specify any criteria for the evaluation of erythroid response in MDS patients, in this study, the assessment of the erythroid response at 12 weeks is performed based on the IWG-2006 criteria ([Appendix 2](#)), which is more widely recognized and used to assess hematologic improvement in anemic patients. An increase in Hb of 1.5 g/dL or more is required for a response. For the assessment of erythroid response, only the hemoglobin component is used and not the reduction of RBC transfusions. As the study population in this trial consists only of patients with low- and Int-1-risk MDS, which receive only few or no transfusions, these patients would otherwise wrongly counted as responders.

2.4 Rationale for choice of combination drugs

Anecdotal case reports and clinical trials suggest that MDS patients can show improvement in hematopoietic function if they receive iron chelation therapy with DFX. In an ad hoc analysis, erythroid response rate during DFX treatment was 22% in 341 MDS patients included in the EPIC trial. This effect of DFX on the hematopoiesis is being studied among others in TELESTO, a prospective randomized study. However, TELESTO patients are selected based on their iron overload status regardless of their history of, or current treatment with EPO. This is the first pilot study to assess the effect in term of erythroid improvement of DFX combined with EPO in patients with low- and int-1-risk MDS.

Serum ferritin levels and also reactive oxygen species (ROS) are both considered to be an important biological factor in the pathogenesis of MDS. DFX iron chelation therapy may be suitable for the reduction of ROS as iron accumulation or severe anemia could contribute to oxidative stress in MDS patients ([Saigo 2011](#)).

Moreover, agents that inhibit NF- κ B are expected to have anticancer and antioxidant properties ([Sarkar 2008](#)). In vitro studies have also shown that DFX is active in attenuating the intracellular levels of NF- κ B, an apoptotic pathway of malignant cells.

The addition of DFX to EPO could harness a potential synergism with the reduction of reactive oxygen species; this may create a better environment in the bone marrow for a better response with EPO.

[figure not shown]
This study is designed to test in a prospective way the combination of DFX with EPO in term of their effect on hematopoiesis in lower-risk MDS patients.

3 Objectives and endpoints

[figure not shown]
[figure not shown]
Objectives and related endpoints are described in [Table 3-1](#) below.

Table 3-1 Objectives and related endpoints

Objective	Endpoint	Analysis
Primary		
To assess the effect of treatment with DFX+EPO vs. EPO alone on erythropoiesis after 12 weeks of treatment	Difference in proportion of patients achieving an erythroid response within 12 weeks of treatment between the two arms according to modified IWG 2006 criteria (increase in Hb \geq 1.5 g/dL)	Refer to Section 10.4
Secondary		
To assess the effect of treatment with DFX+EPO and EPO alone on hematological response within 24 weeks of treatment	Proportion of patients achieving a hematological response within 24 weeks of treatment with DFX+EPO and EPO alone (increase in Hb, improvement of neutropenia and thrombocytopenia) according to modified IWG 2006 criteria	Refer to Section 10.5.1
To assess the effect of treatment on erythropoiesis within 24 weeks in patients that were non-responder to EPO alone within 12 weeks and switched to DFX+EPO	Proportion of patients achieving an erythroid response according to modified IWG 2006 criteria (increase in Hb \geq 1.5 g/dL) within 24 weeks in patients which were non-responder to EPO alone within 12 weeks and switched to DFX+EPO	Refer to Section 10.5.2
To assess the effect of treatment with EPO alone on erythropoiesis after 24 weeks of treatment	Proportion of patients achieving an erythroid response within 24 weeks of treatment with EPO alone (increase in Hb \geq 1.5 g/dL) according to modified IWG 2006 criteria	Refer to Section 10.5.4
To assess time to erythroid response in patients treated with DFX+EPO and patients treated with EPO alone	Time to erythroid response is defined as the time from date of start of treatment to the date of event defined as the first documented response according to modified IWG 2006 criteria (increase in Hb \geq 1.5 g/dL)	Refer to Section 10.5.3
To estimate time to erythroid response in patients who were non-responder to EPO alone after 12 weeks and switched to DFX+EPO	Time to erythroid response is defined as the time from date of switch (start of treatment with the combination) to the date of event , i.e. from week 13 to week 24, defined as the first documented response according to modified IWG 2006 criteria (increase in Hb \geq 1.5 g/dL)	Refer to Section 10.5.5
To estimate time to hematological response in patients treated with DFX+EPO and EPO alone within 24 weeks	Time to hematological response is defined as the time from date of start of treatment to the date of event defined as the first documented response (increase in Hb, improvement of neutropenia and thrombocytopenia) according to modified IWG 2006 criteria	Refer to Section 10.5.6
To estimate duration of erythroid response among responders treated with EPO alone	Duration of erythroid response is defined as the time from onset of the first response to progression/relapse (decrease in Hb \geq 1.5 g/dL from Hb value at response) among responders treated with EPO alone within the whole 24 weeks period	Refer to Section 10.5.7

Objective	Endpoint	Analysis
To estimate duration of erythroid response among responders treated with DFX+EPO	Duration of erythroid response is defined as the time from onset of the first response to progression/relapse (decrease in Hb \geq 1.5 g/dL from Hb value at response) among patients randomized to EPO+DFX up to week 24 and for patients switched from EPO to DFX+EPO from week 13 to week 24	Refer to Section 10.5.8
To evaluate tolerability and safety of the combination	Incidence of adverse events (AEs) overall and by severity, and serious adverse events (SAEs).	Refer to Section 10.5.11
To assess iron parameters in patients randomized to EPO alone, DFX+EPO and in patients randomized to EPO alone and switched to DFX+EPO after 12 weeks	Change in SF from baseline to every visit in patients throughout in the combination arm, throughout in the EPO arm and switched from EPO arm to EPO+DFX after 12 weeks	Refer to Section 10.5.9
To assess Hb parameters in patients randomized to EPO alone, DFX+EPO and in patients randomized to EPO alone and switched to DFX+EPO after 12 weeks	Change in Hb from baseline to every visit in patients throughout in the combination arm, throughout in the EPO arm and switched from EPO arm to DFX+EPO after 12 weeks	Refer to Section 10.5.10
Supportive		
To assess the effect of treatment with DFX+EPO and EPO alone on hematologic improvement within 24 weeks of treatment	Proportion of patients achieving a hematologic improvement (improvement of neutropenia and thrombocytopenia) within 24 weeks of treatment with DFX+EPO and EPO alone	Refer to Section 10.5.1
To assess the effect of treatment with DFX+EPO and EPO alone on total hematological response within 24 weeks of treatment	Proportion of patients achieving a hematological response (increase in Hb, improvement of neutropenia and thrombocytopenia) according to modified IWG 2006 criteria and patients achieving a hematologic improvement (improvement of neutropenia and thrombocytopenia) within 24 weeks of treatment with DFX+EPO and EPO alone	Refer to Section 10.5.1
To estimate time to hematologic improvement in patients treated with DFX+EPO and EPO alone within 24 weeks	Time to hematologic improvement is defined as the time from date of start of treatment to the date of event defined as the first documented hematologic improvement (improvement of neutropenia and thrombocytopenia)	Refer to Section 10.5.6
To estimate time to total hematological response in patients treated with DFX+EPO and EPO alone within 24 weeks	Time to total hematological response is defined as the time from date of start of treatment to the date of event defined as the first documented hematologic improvement (improvement of neutropenia and thrombocytopenia) or hematological response (increase in Hb, improvement of neutropenia and thrombocytopenia) according to modified IWG 2006 criteria	Refer to Section 10.5.6

4 Study design

